4.5.1. Safety Variables

Ciprofloxacin has a well-established safety profile and has been prescribed to several millions of people in the United States (US) and worldwide as it was the CDC's recommended treatment regimen for uncomplicated gonorrhea from 1993 to 2007. Therefore, adverse event assessment is not required for this study.

In order to address the FDA Drug Safety Communication dated May 12, 2016, regarding fluoroquinolone use for certain uncomplicated infections, subjects are asked at Visit 1, Visit 2, and any Unscheduled or Early Termination Visit if they have experienced any serious side effects related to fluoroquinolone use. These include tendon pain, joint pain, muscle pain, tingling or pricking sensation, confusion, and hallucinations. This information is recorded in the study source documents as a change in health status.

Any subject who experiences such an event is given instructions on how to submit a MedWatch Consumer Voluntary Reporting Form to the FDA if they desire.

Side effects of fluoroquinolone use will be summarized for all enrolled subjects (see Section 9).

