9.3. Adverse Events

9.3.1. Side Effects Related to Fluoroquinolone use

Summary of side effects related to fluoroquinolone use will be presented by visits ([Table 34](#)). Individual subject listing will be presented for all side effects related to fluoroquinolone use ([Listing 14](#)).

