If Yes for question 4, did you use a condom or barrier with oral intercourse? ³	No	x	xx	x	xx	x	xx
	Always	x	xx	x	xx	x	xx
	Sometimes	x	xx	x	xx	x	xx
	Unknown	x	xx	x	xx	x	xx
	Refuse to answer	x	xx	x	xx	x	xx
5. Have you had receptive 'bottom' anal intercourse since the last visit?	Yes	x	xx	x	xx	x	xx
	No	x	xx	x	xx	x	xx
	Refuse to answer	x	xx	x	xx	x	xx

Table 33: Summary of Follow-up Categorical Sexual History — All Enrolled Subjects (Continued)

Sexual History Interview Question	Value	Visit 2 (N=X)		Unscheduled Visit (N=X)		All Subjects (N=X)	
		n	%	n	%	n	%
If Yes for question 5, did you use a condom with receptive anal intercourse? ⁴	No	x	xx	x	xx	x	xx
	Always	x	xx	x	xx	x	xx
	Sometimes	x	xx	x	xx	x	xx
	Unknown	x	xx	x	xx	x	xx
	Refuse to answer	x	xx	x	xx	x	xx
6. Have you had insertive ‘top’ anal intercourse since the last visit? (Males only) ⁵	No	x	xx	x	xx	x	xx
	Yes	x	xx	x	xx	x	xx
	Refused to answer	x	xx	x	xx	x	xx
	N/A (if female)	x	xx	x	xx	x	xx
If Yes for question 6, did you use a condom with insertive anal intercourse? ⁶	No	x	xx	x	xx	x	xx
	Always	x	xx	x	xx	x	xx
	Sometimes	x	xx	x	xx	x	xx
	Unknown	x	xx	x	xx	x	xx
	Refuse to answer	x	xx	x	xx	x	xx

N=Number of enrolled subjects at the specific visit.

¹ The denominator of the percentage for this question is the number of subjects answered “yes” for question 2 at each visit.² The denominator of the percentage for this question is the number of subjects answered “yes” for question 3 at each visit.³ The denominator of the percentage for this question is the number of subjects answered “yes” for question 4 at each visit.⁴ The denominator of the percentage for this question is the number of subjects answered “yes” for question 5 at each visit.⁵ The denominator of the percentage for this question is the number of male subjects at each visit.⁶ The denominator of the percentage for this question is the number of male subjects answered “yes” for question 6 at each visit.

Table 34: Side Effects of Fluoroquinolone Use

Summary	Visit 1 (N = x)		Visit 2 (N = x)		Visit 3* (N = x)	
	n	%	n	%	n	%
Tendon Pain	x	xx	x	xx	x	xx
Joint Pain	x	xx	x	xx	x	xx
Muscle Pain	x	xx	x	xx	x	xx
Tingling or Pricking Sensation	x	xx	x	xx	x	xx
Confusion	x	xx	x	xx	x	xx
Hallucinations	x	xx	x	xx	x	xx

N is the number of subjects whose assessments were collected at the particular visit.

'n' represents the number of subjects who reported each sign or symptom at the Visit(s) indicated.

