xxxxxx	Visit 1 (Day 1)/ Visit 2 (Day 5-10)	xxxxxx	Sore throat/Anorectal pain/Anorectal discharge/Anorectal bleeding	Urethral discharge/Pain with urination (Males Only) Abnormal vaginal discharge/Abnormal vaginal bleeding/pain during intercourse (Female Only)	Pharyngeal erythema/Anorectal discharge	Urethral discharge (Males Only) Abnormal cervical discharge (Females Only)

Note: Only some subjects have data at Visit 3 due to the protocol amendment.

1. Implementation Notes:
2. Sort order will be Subject ID, Study Visit.

Listing 13: Compliance Data

Subject ID	Dose Taken?	Vomit Within 1 Hour of Study Drug Administration?	Compliance Status
xxxxxx	Yes/No	Yes/No	Compliant/Non-compliant
xxxxxx	Yes/No	Yes/No	Compliant/Non-compliant
xxxxxx	Yes/No	Yes/No	Compliant/Non-compliant
xxxxxx	Yes/No	Yes/No	Compliant/Non-compliant

Implementation Notes:

1. Sort order will be Subject ID.

Listing 14: Side Effects Related to Fluoroquinolone

Subject ID	Study Visit	Serious Side Effects Related to Fluoroquinolone
xxxxxx	Visit 1 (Day 1)/ Visit 2 (Day 5-10)	Tendon pain/Joint pain/Muscle pain/Tingling or pricking sensation/Confusion/Hallucinations
xxxxxx	Visit 1 (Day 1)/ Visit 2 (Day 5-10)	Tendon pain/Joint pain/Muscle pain/Tingling or pricking sensation/Confusion/Hallucinations
xxxxxx	Visit 1 (Day 1)/ Visit 2 (Day 5-10)	Tendon pain/Joint pain/Muscle pain/Tingling or pricking sensation/Confusion/Hallucinations

Note: Only some subjects have data at Visit 3 due to the protocol amendment.

Implementation Notes:

1. Sort order will be Subject ID, Study Visit.

Listing 15: Baseline Pregnancy Test Results

Subject ID	Was a urine pregnancy test performed?	Pregnancy Test Result
xxxxxxx	Yes/No/NA	Negative/Positive
xxxxxxx	Yes/No/NA	Negative/Positive

Implementation Notes:

1. Sort order is Subject ID

Listing 16: Physical Exam Findings

Study Visit	Actual Study Day	Body System	Abnormal Finding
Visit 1 (Day 1)	x	xxx	xxxxxxxxxxxxxxxxxxxxxx
Visit 2 (Day 5-10)	x	xxx	xxxxxxxxxxxxxxxxxxxxxx

Implementation Notes:

- 1. Sort order will be Subject ID, Study Visit.
- 2. Only abnormal findings will be presented.

Listing 17: Concomitant Medications

Subject ID	CM Number	Medication	Medication Start Day	Medication End Day	Indication	ATC 1/ ATC2
XXXXXX	XX	XXXXXXXX	XX	XX	XXXXXXXX	
XXXXXX	XX	XXXXXXXX	XX	XX	XXXXXXXX	
XXXXXX	XX	XXXXXXXX	XX	XX	XXXXXXXX	

Implementation Notes:

1. Sort order will be Subject ID, CM Number.

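### Table 34, the only side-effect summary, has no place for Unscheduled or Early Termination reports and no rule for separating new symptoms from persisting ones

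*SAP*

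**What the plan says.** Collection: in SAP 4.5.1, "subjects are asked at Visit 1, Visit 2, and any Unscheduled or Early Termination Visit" about tendon, joint and muscle pain, tingling, confusion and hallucinations. Protocol section 9 says the same. Protocol 7.4 puts this history first at both Unscheduled and Early Termination visits, and the Schedule of Events marks it there. Protocol 8.1 places the Visit 1 history before treatment.

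Reporting: SAP 4.5.1 states that "Side effects of fluoroquinolone use will be summarized for all enrolled subjects". SAP 9.3.1 adds that "Summary of side effects related to fluoroquinolone use will be presented by visits", through Table 34, and that "Individual subject listing will be presented for all side effects related to fluoroquinolone use", through Listing 14.

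Shells: "Table 34: Side Effects of Fluoroquinolone Use" has one column each for Visits 1, 2 and 3. A footnote explains that Visit 3 data exist for only some subjects because of a protocol amendment. In its notes, "n' represents the number of subjects who reported each sign or symptom at the Visit(s) indicated", the denominator is subjects assessed at that visit, and one subject may appear under every visit. "Listing 14: Side Effects Related to Fluoroquinolone" shows Visit 1 and Visit 2 as its visit values, with the same Visit 3 note.

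**The concern.** The shell is narrower than the collection schedule. A subject who reports a symptom at an Unscheduled visit and not at Visit 2, or who terminates early and never reaches Visit 2, contributes nothing post-dose to the table. The early terminator also leaves the post-dose denominator, which sits badly with a promised summary of all enrolled subjects.

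Separately, the table's title calls its contents side effects, but the Visit 1 column is pre-dose and the Visit 2 column counts any report. The SAP defines no new-onset or treatment-emergent event, so the table cannot show how many subjects developed a symptom after ciprofloxacin.

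This matters because the plan does not require adverse event assessment and has no formal safety analysis. The symptom questions were included in response to an FDA safety communication, and Table 34 is their only tabulation.

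**Working it through.** The plan states no figure on this point, so there is nothing to reproduce. The first check sets collection against reporting.

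| Contact | Symptoms asked? | Table 34 column? | Visit value in Listing 14 shell? |
|---|---|---|---|
| Visit 1 (pre-dose) | Yes | Yes | Yes |
| Visit 2 | Yes | Yes | Yes |
| Visit 3 | Some subjects (amendment) | Yes | Footnote only |
| Unscheduled | Yes | No | No |
| Early Termination | Yes | No | No |

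Table 33 (follow-up sexual history), immediately before it, does have an Unscheduled Visit column, so leaving such visits out is not a general convention of the shells.

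Could the SAP 4.5 rule for multiple observations bring these reports in? It keeps one record per window, the one closest to schedule. It does not say that an Unscheduled or Early Termination record is assigned to Visit 2. If it were, a record not selected would still drop out of the table.

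The second check is whether the Visit 2 column measures new symptoms. That depends on what is recorded at Visit 2, and the protocol can be read two ways:

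- Section 9 has subjects asked whether they have experienced the symptoms. On that reading a persisting complaint is recorded again.
- Section 8.1 takes the interim history when the subject notes that a symptom has altered since the last visit, and section 9 records reports as an altered health status. On that reading an unchanged complaint may not be recorded at Visit 2. A symptom first reported at an Unscheduled visit and unchanged since might then appear in no column.

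Illustration of the range. From the documents: 381 enrolled. Assumed: all dosed; 10% without Visit 2 (the protocol's 10% is for all per-protocol exclusions, so this is only a stand-in), giving 381 × 0.90 ≈ 343 attending and 38 not; 1% new onset among those free of the symptom at Visit 1; baseline prevalence b of 2%, 5% or 10%; and a fraction c of baseline complaints recorded again at Visit 2.

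Visit 2 column = 343 × [b·c + (1 − b) × 0.01]. New-onset count = 343 × (1 − b) × 0.01.

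| b | c = 0 | c = 0.5 | c = 1 | Truly new |
|---|---|---|---|---|
| 2% | 3.4 | 6.8 | 10.2 | 3.4 |
| 5% | 3.3 | 11.8 | 20.4 | 3.3 |
| 10% | 3.1 | 20.2 | 37.4 | 3.1 |

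With no carry-over the column is right. With full carry-over it shows about 10 to 37 subjects against about 3. In the other direction, each subject whose only report of a symptom came at an Unscheduled or Early Termination visit lowers the table's post-dose count by one.

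Choice of denominator for a new-onset rate: dividing by all 381 dosed gives 3.4/381 = 0.88% (b = 2%) to 3.1/381 = 0.81% (b = 10%), although 1% was assumed. That denominator treats the 38 never assessed as event-free and retains subjects who already had the symptom. Dividing by assessed subjects without the symptom at Visit 1, 343 × (1 − b), returns 1%.

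**The case against.** The strongest answer is that the data will be visible anyway. SAP 9.3.1 promises a listing of all these side effects, and SAP 4.5 says that everything recorded will be listed. The Listing 14 shell is a mock-up, and its Visit 3 footnote shows that its visit values are not exhaustive. This stands in part: the text covers Unscheduled and Early Termination reports, so the shell needs aligning with it, and a loss of data from the listing should not be claimed. It does not repair the summary table.

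Four stronger readings are tempting, and the documents do not support them.

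- A reader might infer that the table mixes pre-dose with post-dose symptoms. It does not: Visit 1 has its own column and denominator and serves as a visible baseline.
- A reader might infer that every persisting complaint is counted again at Visit 2. The wording of Protocol 8.1 and section 9 leaves that open.
- A reader might infer that subjects returning early because of a symptom are systematically lost. The explicit instruction to return early concerns vomiting within an hour, which is not one of the six symptoms. Subjects seen at an Unscheduled visit are reminded to come back and are due to be asked again at Visit 2.
- A reader might infer that Table 34 is all the trial can say about harm. Vomiting is in Listing 13, abnormal examination findings are in Listing 16, and reasons for early termination are listed.

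It is also fair that no hypothesis, sample size or decision rule depends on this table.

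**Conclusion.** The mismatch between collection and reporting is real and can be read directly from the shells: Table 34 has no place for two kinds of visit at which the symptoms are asked about. The missing new-onset rule is also real. Its effect is conditional, running from none to several-fold overstatement of new symptoms at Visit 2, depending on whether unchanged complaints are recorded again. That range rests on assumed prevalence, onset and attendance. The number of events reported only at Unscheduled or Early Termination visits cannot be estimated from the documents.

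The conclusion is that post-dose side effects can be miscounted in the only side-effect summary, not that they will be. This is a low-cost improvement to descriptive safety reporting, with no bearing on the primary or secondary efficacy results.

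**What to change.** 1. Add an Unscheduled/Early Termination column to Table 34.
2. Add a column for any post-dose visit, new since Visit 1. Count each subject once per symptom if it was not reported at Visit 1 and was reported at Visit 2, Visit 3 (where collected), or an Unscheduled or Early Termination visit. The denominator is dosed subjects with at least one post-dose assessment who did not report that symptom at Visit 1. State alongside it the number dosed but never assessed afterwards.
3. State in SAP 9.3.1 whether a complaint unchanged since Visit 1 is recorded at later visits, so that the Visit 2 column can be interpreted.
4. Show Unscheduled and Early Termination visits in the Listing 14 shell, to match SAP 4.5 and 9.3.1.

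The cost is one or two table columns, a sentence of text and a shell edit. No new data collection is needed, since the plan already asks these questions at those visits. One thing to confirm is that the answers from Unscheduled and Early Termination visits reach the study database, because the protocol specifies only that they go into source documents.

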APPENDIX 2. FIGURE MOCK-UPS**LIST OF FIGURES**

Figure 1:	Sample Size/Probability Estimates	66
Figure 2:	CONSORT Flow Diagram	67
Figure 3:	Histogram: MIC distribution for Antimicrobials by Visit— Urethral/Cervical— Micro-ITT population	68
Figure 4:	Histogram: MIC distribution for Antimicrobials by Visit— Rectal— Micro- ITT population	68
Figure 5:	Histogram: MIC distribution for Antimicrobials by Visit— Pharyngeal — Micro-ITT population	68
Figure 6:	Histogram: MIC distribution for Antimicrobials by Visit— Urethral/Cervical — PP population	68
Figure 7:	Histogram: MIC distribution for Antimicrobials by Visit— Rectal— PP population	68
Figure 8:	Histogram: MIC distribution for Antimicrobials by Visit— Pharyngeal — Micro-ITT population	68

[figure not shown]
[figure not shown]
[figure not shown]
Figure 1: Sample Size/Probability Estimates

Figure 2: CONSORT Flow Diagram

**Figure 3: Histogram: MIC distribution for Antimicrobials by Visit—
Urethral/Cervical— Micro-ITT population**

Implementation notes:

The figure will be a paneled figure with specimen as columns and visits as rows.

Figures with similar format:

Figure 4: Histogram: MIC distribution for Antimicrobials by Visit— Rectal— Micro-ITT population

Figure 5: Histogram: MIC distribution for Antimicrobials by Visit— Pharyngeal — Micro-ITT population

Figure 6: Histogram: MIC distribution for Antimicrobials by Visit— Urethral/Cervical — PP population

Figure 7: Histogram: MIC distribution for Antimicrobials by Visit— Rectal— PP population

Figure 8: Histogram: MIC distribution for Antimicrobials by Visit— Pharyngeal — Micro-ITT population

APPENDIX 3. LISTINGS MOCK-UPS**LISTINGS**

Listing 1: Subject Disposition.....	70
Listing 2: Subjects Excluded from Primary Analysis Populations	71
Listing 3: Subject-Specific Protocol Deviations	72
Listing 4: Non-Subject-Specific Protocol Deviations.....	73
Listing 5: Microbiological Results.....	74
Listing 6: Clinical Laboratory Results – Urine Pregnancy Test	75
Listing 7: Individual Efficacy Data.....	76
Listing 8: Demographic and Baseline Characteristics Data—All Enrolled Subjects	77
Listing 9: Sexual History at Baseline Visit—All Enrolled Subjects.....	78
Listing 10: Sexual History at Follow-up Visit—All Enrolled Subjects.....	79
Listing 11: Sexual History at Follow-up Visit—All Enrolled Subjects.....	80
Listing 12: N. Gonorrhoeae Symptomatology.....	81
Listing 13: Compliance Data	82
Listing 14: Side Effects Related to Fluoroquinolone.....	83
Listing 15: Baseline Pregnancy Test Results.....	84
Listing 16: Physical Exam Findings	85
Listing 17: Concomitant Medications.....	86

[illegible]

1. Sort order will be by Subject ID, Category.
2. Category will be “Early Termination” or “Protocol Completed”.
3. In the “Reason for Early Termination” column, concatenate any “specify” fields, including the DV number.

Listing 2: Subjects Excluded from Primary Analysis Populations

Subject ID	Analyses in which Subject is Included	Analyses from which Subject is Excluded	Results Available?	Reason Subject Excluded
XXXXXX	[e.g., ITT, micro-ITT, PP]	[e.g., ITT, micro-ITT, PP]	Yes/No	XXXXX
XXXXXX	[e.g., ITT, micro-ITT, PP]	[e.g., ITT, micro-ITT, PP]	Yes/No	XXXXX
XXXXXX	[e.g., ITT, micro-ITT, PP]	[e.g., ITT, micro-ITT, PP]	Yes/No	XXXXX
XXXXXX	[e.g., ITT, micro-ITT, PP]	[e.g., ITT, micro-ITT, PP]	Yes/No	XXXXX
XXXXXX	[e.g., ITT, micro-ITT, PP]	[e.g., ITT, micro-ITT, PP]	Yes/No	XXXXX

Note: “Yes” in the “Results available” column indicates that available data were removed from the primary analysis. “No” indicates that no data were available for inclusion in the analysis.

Implementation Notes:

1. Sort order will be Subject ID.
2. Reasons Subject excluded should match the same verbiage that is used on the analysis population tables.

Listing 3: Subject-Specific Protocol Deviations

DV Number	Study Day	Deviation	Deviation Category	Reason for Deviation	Deviation Resulted in Subject Termination?	Deviation Resolution	Comments
Subject ID:							
xx	x	xxxxxxxxxx	xxxxxxxxxx	xxxxxxxxxx	Yes/No	xxxxxxx	xxxxxxxxxxxxxxxxxxxxxxxxxxxxxx
xx	x	xxxxxxxxxx	xxxxxxxxxx	xxxxxxxxxx	Yes/No	xxxxxxx	xxxxxxxxxxxxxxxxxxxxxxxxxxxxxx

Implementation Notes:

- 1. Sort order will be by Subject ID, DV number.
- 2. In the “Deviation Category” column concatenate any specify fields.
- 3. In the “Reason for Deviation” column concatenate any “specify” fields.

Listing 4: Non-Subject-Specific Protocol Deviations

Site	Deviation	Start Date	End Date	Reason for Deviation	Deviation Resulted in Subject Termination?	Deviation Category	Deviation Resolution	Comments
xxxx	xxxxxxx	x	x	xxxxxxx	Yes/No	xxxx	xxxxxxx	xxxxxxxxxxxxxxxx
xxxx	xxxxxxx	x	x	xxxxxxx	Yes/No	xxxx	xxxxxxx	xxxxxxxxxxxxxxxx

Implementation Notes:

- 1. Sort order will be by Site Name, Start Date.
- 2. In the “Deviation Category” column concatenate any specify fields.
- 3. In the “Reason for Deviation” column concatenate any “specify” fields.

Listing 5: Microbiological Results

Study Visit	Actual Study Day	Sex	Age (years)	N. gonorrhoeae Culture Result	NAAT Testing Result	gyrA Assay Results	Culture-Based Antimicrobial Susceptibility Testing	Anatomical Site
Subject ID:								
Visit 1 (Day 1)	x	xxxxx	xx	Negative/ Positive/ Indeterminate/ Not Done	Negative/ Positive/ Indeterminate/ Not Done	Wild type gyrA detected/ Mutant gyrA detected/ Indeterminate/ Not Done	Susceptible/ Not susceptible	Urethral/Cervical/ Rectal/Pharyngeal
Visit 2 (Day 5-10)	x	xxxxxx	xx	Negative/ Positive/ Indeterminate/ Not Done	Negative/ Positive/ Indeterminate/ Not Done	Wild type gyrA detected/ Mutant gyrA detected/ Indeterminate/ Not Done	Susceptible/ Not susceptible	Urethral/Cervical/ Rectal/Pharyngeal

Implementation Notes:

1. Sort order will be Subject ID, Study Visit.
2. Subject may have multiple rows for different anatomical sites.

Listing 6: Clinical Laboratory Results – Urine Pregnancy Test

Subject ID	Study Day of Assessment	Collection Day	Was a Urine Pregnancy Test Performed?	Result
XXXXXX	x	x	Yes/No	Negative/ Positive
XXXXXX	x	x	Yes/No	Negative/ Positive
XXXXXX	x	x	Yes/No	Negative/ Positive
XXXXXX	x	x	Yes/No	Negative/ Positive

Implementation Notes:

1. Sort order will be Subject ID.

Listing 7: Individual Efficacy Data

Anatomical Site	N. gonorrhoeae Culture Result at Visit 1	N. gonorrhoeae Culture Result at Visit 2	Microbiological Outcome Status
Subject ID:			
Urethral/ Cervical/ Rectal/ Pharyngeal	Negative/ Positive/ Indeterminate/ Not Done	Negative/ Positive/ Indeterminate/ Not Done	Microbiological Cure/ Microbiological Failure/ Non-evaluable

Implementation Notes:

- 1. Sort order will be Subject ID.

Listing 8: Demographic and Baseline Characteristics Data—All Enrolled Subjects

Subject ID	Sex	Age at Enrollment (years)	Ethnicity	Race
XXXXXX	XXXXXX	XX	XXXXXXX	XXXXXXX
XXXXXX	XXXXXX	XX	XXXXXXX	XXXXXXX
XXXXXX	XXXXXX	XX	XXXXXXX	XXXXXXX
XXXXXX	XXXXXX	XX	XXXXXXX	XXXXXXX

Implementation Notes:

- 1. Sort order will be Subject ID.
- 2. For the “Race” column, if a subject is Multi-Racial, all races will be listed, separated by a comma.

Listing 9: Sexual History at Baseline Visit—All Enrolled Subjects

Subject ID	What is your gender identity?	What is your sexual orientation?	Do you have sex with men, women, transgender men, transgender women, or multiple genders?	Have you had sex (vaginal, anal, or oral) in the past 30 days?
XXXXXX	XXXXX	XXXXXX	XXXXXXX	Yes/No/Refused to answer
XXXXXX	XXXXX	XXXXXX	XXXXXXX	Yes/No/Refused to answer

Implementation Notes:

1. Sort order will be by Subject ID
2. Includes data from Visit 1
3. Note: Specify fields will be concatenated with a “.”.

Listing 10: Sexual History at Follow-up Visit—All Enrolled Subjects

Subject ID	Study Day	1. Have you had sex (vaginal, anal, or oral) since the last visit	2. Have you had vaginal intercourse since the last visit	If Yes for question 2, did you use a condom with vaginal intercourse?	3. Have you given oral intercourse since the last visit	If Yes to question 3, did you use a condom or barrier with oral intercourse?
xxxxxx	xx	Yes/No/Refused to answer	Yes/No/Refused to answer	No/Always/Sometimes/Unknown/ Refused to answer	Yes/No/Refused to answer	No/Always/Sometimes/ Unknown/ Refused to answer
xxxxxx	xx	Yes/No/Refused to answer	Yes/No/Refused to answer	No/Always/Sometimes/Unknown/ Refused to answer	Yes/No/Refused to answer	No/Always/Sometimes/ Unknown/ Refused to answer

Implementation Notes:

- Sort order will be by Subject ID, Study Day
- For questions that are parented, if the parent question is “No” and the subsequent fields are not required, fill the cell with “—”

Listing 11: Sexual History at Follow-up Visit—All Enrolled Subjects

Subject ID	Study Day	4. Have you received oral intercourse since the last visit	If Yes to question 4, did you use a condom or barrier with oral intercourse?	5. Have you had receptive 'bottom' anal intercourse since the last visit	If Yes to question 5, did you use a condom with receptive anal intercourse	If Yes to question 5, did you use a condom with insertive anal intercourse	6. Have you had insertive 'top' anal intercourse since the last visit? (Males only)	If Yes to question 6, did you use a condom with insertive anal intercourse?
xxxxxx	xx	Yes/No/ Refused to answer	No/Always/Sometimes/ Unknown/ Refused to answer	Yes/No/ Refused to answer	No/Always/Sometimes/ Unknown/ Refused to answer	No/Always/Sometimes/ Unknown/ Refused to answer	No/Yes/ Refused to answer/ NA (if female)	No/Always/Sometimes/ Unknown/ Refused to answer
xxxxxx	xx	Yes/No /Refused to answer	No/Always/Sometimes/ Unknown/ Refused to answer	Yes/No/ Refused to answer	No/Always/Sometimes/ Unknown/ Refused to answer	No/Always/Sometimes/ Unknown/ Refused to answer	No/Yes/ Refused to answer/ NA (if female)	No/Always/Sometimes/ Unknown/ Refused to answer

Implementation Notes:

1. Sort order will be by Subject ID, Study Day
2. For questions that are parented, if the parent question is “No” and the subsequent fields are not required, fill the cell with “—”

Listing 12: *N. Gonorrhoeae* Symptomatology

Subject ID	Study Visit	Sex	Symptoms of Gonorrhea	Gender specific Symptoms of Gonorrhea	Signs of Gonorrhea	Gender specific Sign of Gonorrhea
xxxxxx	Visit 1 (Day 1)/ Visit 2 (Day 5-10)	xxxxxx	Sore throat/Anorectal pain/Anorectal discharge/Anorectal bleeding	Urethral discharge/Pain with urination (Males Only) Abnormal vaginal discharge/Abnormal vaginal bleeding/pain during intercourse (Female Only)	Pharyngeal erythema/Anorectal discharge	Urethral discharge (Males Only) Abnormal cervical discharge (Females Only)
xxxxxx	Visit 1 (Day 1)/ Visit 2 (Day 5-10)	xxxxxx	Sore throat/Anorectal pain/Anorectal discharge/Anorectal bleeding	Urethral discharge/Pain with urination (Males Only) Abnormal vaginal discharge/Abnormal vaginal bleeding/pain during intercourse (Female Only)	Pharyngeal erythema/Anorectal discharge	Urethral discharge (Males Only) Abnormal cervical discharge (Females Only)
xxxxxx	Visit 1 (Day 1)/ Visit 2 (Day 5-10)	xxxxxx	Sore throat/Anorectal pain/Anorectal discharge/Anorectal bleeding	Urethral discharge/Pain with urination (Males Only) Abnormal vaginal discharge/Abnormal vaginal bleeding/pain during intercourse (Female Only)	Pharyngeal erythema/Anorectal discharge	Urethral discharge (Males Only) Abnormal cervical discharge (Females Only)

Note: Only some subjects have data at Visit 3 due to the protocol amendment.

1. Implementation Notes:
2. Sort order will be Subject ID, Study Visit.

Listing 13: Compliance Data

Subject ID	Dose Taken?	Vomit Within 1 Hour of Study Drug Administration?	Compliance Status
xxxxxx	Yes/No	Yes/No	Compliant/Non-compliant
xxxxxx	Yes/No	Yes/No	Compliant/Non-compliant
xxxxxx	Yes/No	Yes/No	Compliant/Non-compliant
xxxxxx	Yes/No	Yes/No	Compliant/Non-compliant

Implementation Notes:

1. Sort order will be Subject ID.

Listing 14: Side Effects Related to Fluoroquinolone

Subject ID	Study Visit	Serious Side Effects Related to Fluoroquinolone
xxxxxx	Visit 1 (Day 1)/ Visit 2 (Day 5-10)	Tendon pain/Joint pain/Muscle pain/Tingling or pricking sensation/Confusion/Hallucinations
xxxxxx	Visit 1 (Day 1)/ Visit 2 (Day 5-10)	Tendon pain/Joint pain/Muscle pain/Tingling or pricking sensation/Confusion/Hallucinations
xxxxxx	Visit 1 (Day 1)/ Visit 2 (Day 5-10)	Tendon pain/Joint pain/Muscle pain/Tingling or pricking sensation/Confusion/Hallucinations

Note: Only some subjects have data at Visit 3 due to the protocol amendment.

Implementation Notes:

1. Sort order will be Subject ID, Study Visit.

Listing 15: Baseline Pregnancy Test Results

Subject ID	Was a urine pregnancy test performed?	Pregnancy Test Result
xxxxxxx	Yes/No/NA	Negative/Positive
xxxxxxx	Yes/No/NA	Negative/Positive

Implementation Notes:

1. Sort order is Subject ID

Listing 16: Physical Exam Findings

Study Visit	Actual Study Day	Body System	Abnormal Finding
Visit 1 (Day 1)	x	xxx	xxxxxxxxxxxxxxxxxxxxxx
Visit 2 (Day 5-10)	x	xxx	xxxxxxxxxxxxxxxxxxxxxx

Implementation Notes:

- 1. Sort order will be Subject ID, Study Visit.
- 2. Only abnormal findings will be presented.

Listing 17: Concomitant Medications

Subject ID	CM Number	Medication	Medication Start Day	Medication End Day	Indication	ATC 1/ ATC2
XXXXXX	XX	XXXXXXXX	XX	XX	XXXXXXXX	
XXXXXX	XX	XXXXXXXX	XX	XX	XXXXXXXX	
XXXXXX	XX	XXXXXXXX	XX	XX	XXXXXXXX	

Implementation Notes:

1. Sort order will be Subject ID, CM Number.
